4 STUDY POPULATION

4.1 Population

Adult patient undergoing elective robot assisted radical prostatectomy

4.2 Inclusion criteria

To participate in this trial, a subject must meet all of the following criteria:

- Age \geq 18 years
- Undergoing elective robot assisted radical prostatectomy (RARP)
- Obtained informed consent

4.3 Exclusion criteria

A potential subject will be excluded from participation when meeting any of the following criteria:

- Laparoscopic radical prostatectomy without robot assistance
- Insufficient control of the Dutch language to read the patient information and to fill out de questionnaires
- (Chronic) use of immunosuppressive medication
- Chronic use of NSAID's and/or opioids or psychotropic drugs
- Use of NSAID's shorter than 5 days before surgery
- Severe liverdisease (Child-Pugh B and C) or chronic kidney disease (stage 4 and 5)
- Neuromuscular disease
- Hyperthyroidism or thyroid adenomas
- Deficiency of vitamin K dependent clotting factors or coagulopathy
- Planned diagnostics or treatment with radioactive iodine < 1 week after surgery
- Indication for rapid sequence induction
- BMI $>35\text{kg/m}^2$
- Known of suspected hypersensitivity to ICG, sodium iodide, iodine, rocuronium or sugammadex
- Use of medication interfering with ICG absorption as listed in the summary of product characteristics (SPC); anticonvulsants, bisulphite compounds, haloperidol, heroin, meperidine, metamizol, methadone, morphium, nitrofurantoin, opium alkaloids, phenobarbital, phenylbutazone, cyclopropane, probencid.

4.4 Sample size calculation

The main study includes 48 patients per study arm (low impact and standard laparoscopy). With this number of patients we will have sufficient power for the primary and secondary analyses:

- 1) Quality of recovery at POD 1 as reflected by the QoR-40 questionnaire. Although Myles et al. reported a minimal clinically relevant difference (MCID) of 6.3 for the QoR-40 questionnaire, consensus about the MCID is lacking. As 6.3 is a relatively small difference on a scale ranging from 40-200, we feel that a MCID of 10 points is more appropriate. A sample size of 48 patients per group is needed to provide 90% power to detect a 10 point difference in the QoR-40 at POD 1 (alpha 5%) with an estimated standard deviation of 15.
- 2) Innate immune function as reflected by the *ex vivo* release of IL-6 and IL-10 upon LPS stimulated leukocytes at POD 7. A sample size of 45 patients per group is needed to provide 90% power to detect a 3.000 pg/mL difference in IL-6 release (alpha 2.5%) with an estimated standard deviation of 4.000 pg/mL at POD 7. A sample size of 42 patients per group is needed to provide 90% power to detect a 50 pg/mL difference in IL-10 release (alpha 2.5%) with an estimated standard deviation of 65 pg/mL. As two cytokines are measured, a Bonferroni correction was used (alpha 2.5%).

5 TREATMENT OF SUBJECTS

5.1 Investigational product/treatment

The head practitioner will ask the patient for permission to let the researcher contact and inform him. After informed consent is given the participants will be randomly assigned in a 1:1 fashion to:

- Experimental group: low impact laparoscopy (low pressure (8 mmHg) and deep NMB (PTC 1-2))
- Control group: standard laparoscopy (standard pressure (14 mmHg) and moderate NMB (TOF 1-2))

At the start of surgery, after intra-abdominal insufflation, ICG injection will take place with peritoneal perfusion, and a parietal peritoneal biopsy will be taken. At the end of surgery a second parietal peritoneum biopsy will be taken.

Perioperative ERAS protocol

A standardized perioperative ERAS protocol is used for this study. Adherence of ERAS key elements (27) as presented by the ERAS society will be scored.

Anesthesia protocol and titration of intra-abdominal pressure

Standardized anesthesia protocol:

- Premedication according to local protocol
- No epidural anesthesia: if conversion to open surgery is necessary, epidural anesthesia can be given postoperatively according to the preference of the attending anesthesiologist.
 - General anesthesia will be achieved with Total Intravenous Anesthesia (TIVA), consisting of propofol bolus 1-3 mg/kg and maintenance aimed at a bispectral index score between 45 and 55, remifentanil 0,25-2mcg/kg/min, lidocaine 1% 1-1,5mg/kg bolus followed by 0,5-3mg/kg/h and esketamine bolus 0,25-1mg/kg.
 - Dexamethason is avoided to prevent influencing the immune response
 - Neuromuscular monitoring is initiated, after the set-up and calibration procedures, with rocuronium (intubation dose 0,6mg/kg). Tracheal intubation is performed 2 minutes after administration in all groups.
 - Postoperative pain management will be paracetamol and oxycodone or patient controlled analgesia (PCA) with morphine.
- After introduction of the camera trocar, insufflation of carbon dioxide is titrated to an IAP of 8mmHg in the experimental group, and 14 mmHg in the control group. After placement of the last trocar the injection of ICG and video registration of peritoneum will take place, and a peritoneal biopsy will be taken. There after surgery will take place, for dissection of the venous plexus, IAP is titrated to 14 mmHg in the experimental group and 20mmHg in the controle group. A second parietal peritoneum biopsy will be taken at the end of surgery. If surgical conditions remain compromised despite adequate pressure and neuromuscular block, the surgeon can decide to convert to an open- or hand-assisted procedure.
- Neuromuscular monitoring is initiated after set-up and calibration procedures.
 - The control group with standard laparoscopy will be monitored with TOF count every 5 minutes in standardized fashion. After intubation, a bolus or continuous infusion of rocuronium is administered as normally done in clinical practice, titrating towards TOF count 1-2. When TOF count is 0, infusion of rocuronium will be stopped until neuromuscular function is recovered to maximal TOF 2.
 - The experimental group with low impact laparoscopy will be monitored with PTC every 5 minutes. After intubation, continuous infusion of rocuronium (0,3-0,4mg/kg) is started and titrated towards PTC 1-2. When PTC is 0, continuous infusion of rocuronium will be decreased, not stopped, until a PTC of 1-2 is reached.
- During surgery patients are ventilated by pressure-regulated volume-controlled ventilation through an endotracheal tube with a mixture of oxygen in air, PEEP of 5cmH₂O and tidal volumes between 6-8ml/kg. Minute ventilation is adjusted to main end-tidal carbon dioxide between 31-43mmHg by changing respiratory rate. Oxygenation is adjusted to main saturation between 97-100% by changing the mixture of oxygen in air.
- According to local protocol a nasogastric tube will be placed for gastric decompression.
- Minimal infusion of fluids and losses will be replaced.
- Core temperature is measured continuously, aiming at 36-37 C.
- The use of drains is avoided

- After skin closure, the NMB is reversed using sugammadex 4mg/kg in the experimental group, and 2mg/kg in the control group unless the TOF ratio is >0,9. If neuromuscular function has recovered spontaneously in the control group, no sugammadex will be administered.
- Extubation will be performed when TOF ratio is stable at >0,9 for more than 2 minutes and the patient is fully awake.

5.2 Use of co-intervention (if applicable)

Not applicable

5.3 Escape medication (if applicable)

Not applicable

6 NON-INVESTIGATIONAL PRODUCT

Not applicable

7 INVESTIGATIONAL PRODUCT

7.1 Name and description of non-investigational product(s)

- a. Rocuronium 10 mg/ml solution for infusion. Rocuronium bromide is indicated as an adjunct to general anaesthesia to facilitate tracheal intubation during routine sequence induction and to provide skeletal muscle relaxation during surgery.
- b. Sugammadex (Bridion®) 100 mg/mL solution for injection. Bridion reverses neuromuscular blockade induced by rocuronium or vecuronium in adults, by selective binding with the relaxant agent.

7.2 Summary of findings from non-clinical studies

- a. Rocuronium: preclinical data reveal no special hazard for humans based on conventional studies of safety pharmacology, repeated dose toxicity, genotoxicity, toxicity to reproduction and development. Carcinogenicity studies have not been performed with rocuronium bromide (28).
- b. Sugammadex: preclinical data reveal no special hazard for humans based on conventional studies of safety pharmacology, repeated dose toxicity, genotoxicity potential, and toxicity to reproduction, local tolerance or compatibility with blood. Sugammadex is rapidly cleared in preclinical species, although residual sugammadex was observed in bone and teeth of juvenile rats. Preclinical studies in young adult and mature rats demonstrate that sugammadex does not adversely affect tooth colour or bone quality, bone structure, or bone metabolism. Sugammadex has no effects on fracture repair and remodelling of bone (29).

7.3 Summary of findings from clinical studies

- a. Rocuronium: the standard intubation dose for geriatric patients and patients with hepatic and/or biliary tract disease and/or renal failure during routine anaesthesia is 0.6mg/kg rocuronium bromide. Regardless of the anaesthetic technique used, the recommended infusion rate is 0.3-0.4 mg/kg/h. For children and adolescents the recommended intubation dose during routine anaesthesia and maintenance dose are similar to those in adults. When used in overweight or obese patients (defined as patients with a body weight of 30% or more above ideal body weight) doses should be reduced taking into account ideal body weight. The following conditions may influence the pharmacokinetics and/or pharmacodynamics of Rocuronium: hepatic and/or biliary tract disease and renal failure, prolonged circulation time, neuromuscular

disease, hypothermia, obesity, burns, hypokalaemia, hypermagnesaemia, hypocalcaemia, hypoproteinaemia, dehydration, acidosis, hypercapnia and cachexia (28).

- b. Sugammadex: the use of sugammadex in patients with severe renal impairment (including patients requiring dialysis ($\text{CrCl} < 30 \text{ mL/min}$)) is not recommended. Studies in patients with severe renal impairment do not provide sufficient safety information to support the use of sugammadex in these patients. For mild and moderate renal impairment (creatinine clearance ≥ 30 and $< 80 \text{ mL/min}$): the dose recommendations are equal to adults without renal impairment. In obese patients, the dose of sugammadex should be based on actual body weight. For mild to moderate hepatic impairment no dose adjustments is required, as sugammadex is mainly excreted renally (29).

7.4 Summary of known and potential risks and benefits

- a. Rocuronium: the most commonly occurring adverse drug reactions include injection site pain/reaction, changes in vital signs and prolonged neuromuscular block. The most frequently reported serious adverse drug reactions during post-marketing surveillance is 'anaphylactic and anaphylactoid reactions' and associated symptoms (28).
- b. Sugammadex: sugammadex is administered concomitantly with neuromuscular blocking agents and anaesthetics in surgical patients. The causality of adverse events is therefore difficult to assess. The most commonly reported adverse reactions in surgical patients were cough, airway complication of anaesthesia, anaesthetic complications, procedural hypotension and procedural complication (common ($\geq 1/100$ to $< 1/10$).

System organ class	Frequencies	Adverse reactions (preferred terms)
Immune system disorders	Uncommon	Drug hypersensitivity reactions
Respiratory, thoracic and mediastinal disorders	Common	Cough
Injury, poisoning and procedural complications	Common	Airway complication of anaesthesia Anaesthetic complication Procedural hypotension Procedural complication

The following adverse reactions were reported in placebo controlled trials where subjects received anaesthesia and/or neuromuscular blocking agents (1,078 subject exposures to sugammadex versus 544 to placebo) (29):

[Very common ($\geq 1/10$), common ($\geq 1/100$ to $<1/10$), uncommon ($\geq 1/1.000$ to $<1/100$), rare ($\geq 1/10.000$ to $<1/1.000$), very rare ($<1/10.000$)]

Fusidic acid and flucloxacillin can cause displacement of sugammadex and should not be administered 6 hours after administration of sugammadex. Sugammadex can also encapsulate hormonal contraceptives, which may leave them less effective (30). Therefore, sugammadex use should be considered as one missed dose of hormonal contraceptive (but this issue is not applicable in this study)

7.5 Description and justification of route of administration and dosage

- a. Rocuronium: rocuronium bromide is administered intravenously (i.v.) either as a bolus injection or as a continuous infusion. The standard intubating dose during routine anaesthesia is 0.6 mg rocuronium bromide per kg body weight, which results in adequate intubation conditions within 60 seconds in nearly all patients. If rocuronium bromide is administered by continuous infusion, it is recommended to give a loading dose of 0.6 mg rocuronium bromide per kg body weight and, when the neuromuscular block starts to recover, to start administration by infusion. In adults under intravenous anaesthesia, the infusion rate required to maintain the neuromuscular block ranges from 0.3 - 0.6 mg/kg/h. Under inhalational anaesthesia the infusion rate ranges from 0.3 - 0.4 mg/kg/h (28).
- b. Sugammadex: sugammadex should be administered intravenously as a single bolus injection. A dose of 4 mg/kg sugammadex is recommended if recovery has reached at least 1-2 post-tetanic counts (PTC) following rocuronium or vecuronium induced blockade. A dose of 2 mg/kg sugammadex is recommended, if spontaneous recovery has occurred up to at least the reappearance of T2 following rocuronium or vecuronium induced blockade (29).

7.6 Dosages, dosage modifications and method of administration

- a. Rocuronium: in both groups, a bolus of 0.6 mg/kg rocuronium is administered intravenously before tracheal intubation. After tracheal intubation, in group A (low pressure with deep NMB), a bolus of 0.6 mg/kg rocuronium is administered and continuous infusion of rocuronium (0.4 mg/kg) is started and titrated towards PTC 1-2. In group B (normal pressure with moderate NMB), a bolus or continuous infusion of rocuronium is administered, titrating towards a TOF count of 1-2. Dosage in both groups is within normal therapeutical range used in clinical practice (28).
- b. Sugammadex: if TOF-ratio is <0.9 the NMB is reversed with an intravenous bolus injection of 2 (moderate NMB) or 4 (deep NMB) mg/kg. If TOF-ratio > 0.9 the patient can be extubated safely (29).

7.7 Preparation and labelling of non-investigational medicinal product

Sugammadex will be provided by MSD. Both Rocuronium and Sugammadex will be prepared and labelled at the Radboudumc pharmacy. The clinical trials unit of the Radboudumc pharmacy will distribute batches of Rocuronium and Sugammadex to the pharmacy of the Canisius Wilhelmina hospital by courier.

7.8 Drug accountability

Administration of stock, preparation and labelling, distribution of batches and returns will be coordinated and logged by the clinical trials unit of the Radboudumc pharmacy. Locally, in the Canisius Wilhelmina hospital, drug registration will be logged on patient level (e.g. batch and ampoule number for each patient).

8 METHODS

8.1 Main study endpoints

- Quality of recovery score (QoR-40) at postoperative day 1.
- IL-6 response upon whole blood LPS stimulation at postoperative day 10-12
- Perfusion index of the parietal peritoneum as calculated from the slope of ICG fluorescence intensity, and time to maximal intensity in seconds. (extracted from video registration).

8.2 Other study parameters

General

- Baseline parameters as age, gender, length, weight, body mass index, comorbidity, indication for and type of surgery.
- Intraoperative parameters routinely measured (at administration of ICG): blood pressure, temperature and level of NMB (train of four response).

Questionnaires

- Quality of recovery score (QoR-40) at 1 day before surgery and day 10-12 after surgery.
- SF-36 general health questionnaire (Dutch version) 1 day before surgery, day 10-12 and 3 months after surgery.
- McGill pain Questionnaire 3 months after surgery

Pain scores

- Pain at rest and movement (NRS 0-10) at 1, 8, 24, 72 hours after surgery
- Is pain acceptable (yes/no) at 1, 8, 24, 72 hours after surgery
- Referred shoulder pain (yes/no) at 1, 8, 24, 72 hours after surgery

PONV

- PONV (yes/no) at 1, 8, 24 and 72 hours after surgery

Medication use

- Cumulative opiate use
- Cumulative use of other analgesics and anti-emetics

Clinical parameters

- Time to reach discharge criteria*
- Length of hospital stay
- Surgical conditions: Leiden Surgical Rating Scale to quantify the quality of the surgical field during the pneumoperitoneum phase (after introduction of the Hasson trocar, after introduction of the third trocar and then every 15 minutes)
- Postoperative complications scored by Clavien Dindo classification (table 2 (1))

Immune function

- Peritoneal mesothelial hypoxia as reflected by peritoneal HIF1-alfa mRNA expression
- Histological peritoneal mesothelial cell injury.
- Plasma levels of DAMPs, cytokines and ex vivo immune function at baseline, 24 hours after surgery and 10-12 days after surgery.

*discharge criteria are: adequate pain control with oral medication, passage of flatus or defecation, intake of solid food tolerated, patient is mobilized and independent and patient accepts discharge. Discharge criteria will be evaluated daily. If the donor for social reasons wants to stay longer (e.g. long distance from partner of child who are still hospitalized) the 'virtual' discharge date is listed. A physician who is independent and blinded (ward physician) is responsible for the actual discharge date.

8.3 Study procedures

Randomization:

Computer-generated randomization (supported by our statistician) will be used with stratification for center. To ensure a balanced distribution, we will use block randomization.

Blinding and treatment allocation:

Blinding of the surgeons to the level of pressure and NMB is ensured by facing monitoring equipment away or covering these under sterile drapes. The level IAP will be set and adjusted by the anesthesiologist who is not blinded to the allocation of treatment. Surgical conditions will be assessed after introduction of the trocars, every 15 minutes or when the surgeon indicates inadequate surgical conditions. When SRS is ≤ 3 (table 1), pressure is increased with 2mmHg to max 14mmHg in group A and B or 16mmHg in group C and D. The anesthesiologist (not blinded) or his/her assistant titrates the dose of rocuronium to the desired level of NMB. The nerve stimulator and computer are placed behind the sterile drapes away from the surgeons. The research physician alongside the anesthetic staff will not be blinded in order to ensure depth of the NMB is continuously adequately monitored. To minimize the risk of observer bias and/or unblinding of the entire team, the following measures will be taken: Surgical adverse events will be registered directly after surgery by the blinded, primary surgeon. Surgeons, scrub nurses, postoperative care nurses, and ward physicians are blinded. Postoperative clinical outcomes (e.g. QoR-40 questionnaires) are collected by a blinded researcher.

Perioperative procedures:

The peri-operative flowchart is shown in figure 6.

During insufflations of the abdomen, the insufflator will be set at an intra-abdominal pressure of 8 or 14 mmHg. The usual dose of indocyanine green (0.2mg/kg) as regularly used will be injected intravenously. The camera trocar is aimed at the lateral abdominal wall and video is recorded for 3 minutes.

An overview of measurements and questionnaires for the primary and secondary endpoints, are given in table 3. Assessment of pain, PONV, discharge criteria and postoperative complications are part of normal medical treatment. Extra for this study, patients are asked to complete the QoR-40, SF-36 and McGill questionnaire. For the secondary endpoints on immune function, blood samples (a standard 6ml lithium/heparine, 10 ml EDTA tube and 2.5ml

Paxgene RNA tube) will be combined with routine laboratory assessment as much as possible. Otherwise, blood will be drawn by vena puncture. Peritoneal biopsy will be performed during laparoscopy when the patient is under anesthesia and peritoneal tissue is directly visible and easily accessible. A biopsy will be taken as previously described and performed by Schaefer et al. (31) and Williams et al. (32) at the start and end of surgery. Briefly, a small part of the parietal peritoneum (0.5-1 x 0.5-1 cm, 2-4mm deep) tissue sample is excised. Half of the sample is fixed and used for histology the other half is used to determine HIF1 α mRNA expression.

Withdrawal of individual subjects

Subjects can leave the study at any time for any reason if they wish to do so without any consequences. The investigator can decide to withdraw a subject from the study for urgent medical reasons or with one of the following criteria:

- Before operation (for example postponement or adjustment of operation)
- During surgery (for example conversion to open procedure)
- After surgery (for example non response to questionnaire)

In case of withdrawal the patient will not be followed. Patients withdrawing will be replaced, with a maximum of 10 patients.

Premature termination of the study

Not applicable

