3 STUDY DESIGN

A mono-center blinded randomized controlled clinical trial at the Canisius Wilhelmina Hospital in Nijmegen, where approximately 300 robot assisted radical prostatectomy (RARP) procedures are performed annually. We expect that the screening and inclusion period (recruitment period) will be 15 months.

Treatments to be compared

- Experimental group: *Low impact laparoscopy*; low pressure PNP (8 mmHg) and deep NMB and reversal of NMB with sugammadex 4mg/kg.

- Control group: *Standard laparoscopy*; standard pressure PNP (14 mmHg) and moderate NMB and spontaneous recovery of neuromuscular function (only if one or more additional boluses of rocuronium are required, it is allowed to reverse with sugammadex 2mg/kg)

All study endpoints will be arbitrated by a blinded researcher. Also the perfusion index is extracted from video registration with MATLAB (R2017a version 9.2.0) by a researcher blinded to the level of pressure and NMB depth.

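### Section 8.3 lets randomised patients be withdrawn after conversion or questionnaire non-response, ends their follow-up and replaces up to 10, while section 10 names no analysis set or missing-data method

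*Combined protocol and SAP*

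**What the plan says.** Section 5.1 places randomisation directly after consent: "After informed consent is given the participants will be randomly assigned in a 1:1 fashion to" the two arms. Any withdrawal during or after surgery is therefore a post-randomisation exit.

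Under its withdrawal heading, section 8.3 says the investigator may withdraw a subject for urgent medical reasons or on listed criteria. Two of these are "During surgery (for example conversion to open procedure") and "After surgery (for example non response to questionnaire"). The consequence is: "In case of withdrawal the patient will not be followed. Patients withdrawing will be replaced, with a maximum of 10 patients".

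On conversion, section 5.1 says: "If surgical conditions remain compromised despite adequate pressure and neuromuscular block, the surgeon can decide to convert to an open- or hand-assisted procedure".

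On blinding, section 3 says "All study endpoints will be arbitrated by a blinded researcher" and section 8.3 says "Postoperative clinical outcomes (e.g. QoR-40 questionnaires) are collected by a blinded researcher". Section 8.3 also blinds the surgeon, but adds: "The research physician alongside the anesthetic staff will not be blinded".

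Section 10 gives ANCOVA adjusted for age and gender, the significance thresholds and a list of secondary parameters. It says that unblinding follows completion of follow-up and identification of protocol violations, but not what is then done with the patients concerned. It names no analysis set, missing-data method or sensitivity analysis.

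**The concern.** Conversion follows from surgical conditions, and the randomised factors, pressure and block depth, can affect those conditions. Failure to return a recovery questionnaire may reflect how the patient is recovering. A rule that removes patients on these grounds can select on arm or outcome, and recruiting others in their place brings back the count but not the balance that randomisation gave.

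The rule also turns one problem into several. A converted patient can still complete a QoR-40 on POD 1 and give a later blood sample. A patient who misses a questionnaire can still give blood. Once follow-up has stopped, those values cannot be recovered at analysis. With no stated analysis set, the decision on who counts in each primary comparison is left until the data exist.

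**Working it through.** **1. Which primary data the rule can lose.** Timings are from sections 5.1, 8.1, 8.2 and Table 3.

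| Primary endpoint | When measured | Effect of withdrawal |
|---|---|---|
| ICG perfusion | After the last trocar, before the dissection | Already recorded; later conversion does not lose it |
| QoR-40 | POD 1 | Lost if withdrawn before POD 1, as at conversion. If withdrawn for not returning this form, it is missing with or without the rule. If withdrawn later, it is already in hand |
| LPS response | Day 7 (synopsis, 4.4, 10.1) or day 10-12 (8.1, 8.2, Table 3) | Lost for anyone withdrawn earlier, including POD 1 non-responders; on either timing it falls after POD 1 |

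Questionnaires and complications scheduled after withdrawal are lost as well.

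**2. The plan's own figures.** Inputs are from section 4.4, with 90% power and a two-sided test. Formula: n per arm = 2 × (z for alpha + z for power)² × (SD/difference)².

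- QoR-40: 2 × (1.960 + 1.282)² × (15/10)² = 47.3, so 48. The plan states 48.
- IL-6: 2 × (2.241 + 1.282)² × (4,000/3,000)² = 44.1, so 45. The plan states 45.
- IL-10: 2 × (2.241 + 1.282)² × (65/50)² = 41.9, so 42. The plan states 42.

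The sample-size arithmetic is sound. No dropout rate is given, so replacement is the only cover for loss.

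**3. Size of the bias (illustration).** The documents give no conversion, withdrawal or non-response rate, so the splits and gaps here are assumptions. Suppose kA and kB patients are withdrawn and replaced, 48 per arm are analysed, and the withdrawn would have scored D worse than those analysed. Then

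bias = D × [kA/(48 + kA) − kB/(48 + kB)].

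QoR-40, D = 20, 3 v 1: 20 × (3/51 − 1/49) = 0.77 points. The standard error is 15 × √(2/48) = 3.06, so the shift is 0.25 standard errors. With no true effect over all randomised patients, the two-sided t-test (94 df) then rejects 5.7% of the time.

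IL-6, D = 4,000 (1 SD), 3 v 1: 4,000 × (3/51 − 1/49) = 154 pg/mL. The standard error is 816, so the shift is 0.19 standard errors. The rejection rate is 2.8%.

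| Endpoint (threshold) | Gap D | Split | Bias | Type I error |
|---|---|---|---|---|
| QoR-40 (5%) | any | even | 0 | 5.0% |
| QoR-40 | 10 | 3 v 1 | 0.4 | 5.2% |
| QoR-40 | 20 | 1 v 0 | 0.4 | 5.2% |
| QoR-40 | 20 | 2 v 0 | 0.8 | 5.8% |
| QoR-40 | 20 | 3 v 1 | 0.8 | 5.7% |
| QoR-40 | 20 | 7 v 3 | 1.4 | 7.3% |
| IL-6 (2.5%) | any | even | 0 | 2.5% |
| IL-6 | 1 SD | 3 v 1 | 154 pg/mL | 2.8% |
| IL-6 | 1 SD | 7 v 3 | 274 pg/mL | 3.3% |
| IL-6 | 1.5 SD | 3 v 1 | 230 pg/mL | 3.1% |
| IL-6 | 1.5 SD | 7 v 3 | 411 pg/mL | 4.4% |

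For IL-10, a 1 SD gap gives 2.5 pg/mL (3 v 1) or 4.5 pg/mL (7 v 3), with the same error rates as IL-6.

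The QoR-40 rows count only patients withdrawn before POD 1 whose score was obtainable, so 7 v 3 would need ten such patients.

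The bias can also hide an effect. Against a true 3,000 pg/mL IL-6 difference with a 1 SD gap, power falls from 92% to 88% (3 v 1) or 85% (7 v 3).

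**The case against.** The case against has real weight.

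- **Withdrawal is discretionary.** Conversion and non-response are examples of when the investigator may withdraw. A reader might infer that primary data are sure to be lost. The documents do not support that: if nobody is withdrawn, nothing is lost. The statement is conditional on use of the rule.
- **The link between arm and conversion is weakened.** The surgeon is blinded. Section 8.3 also provides for raising the pressure when surgical conditions are rated 3 or lower, up to 14 mmHg in group A, and section 5.1 allows conversion only when conditions stay compromised despite adequate pressure and block. (The same sentence in 8.3 refers to groups C and D, which this trial does not have, and needs reconciling.) This makes a difference between arms less likely but does not exclude one.
- **Both named triggers arise with blinded people.** The surgeon decides on conversion and a blinded researcher collects the questionnaires. But blinding protects how outcomes are measured, not who stays to be measured. Section 8.3 does not say that the withdrawal decision is blind, and some study staff know the allocation.
- **The effect is probably small.** The moderate rows above bear this out.

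A reader might also infer that data already collected from withdrawn patients are thrown away. Section 8.3 does not say so; the gap is that section 10 does not say they are used.

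A third tempting reading puts all ten replaced patients in one arm with a 20-point gap: 20 × 10/58 = 3.4 points and a type I error near 20%. Nothing documented supports that split or gap, and it counts QoR-40 scores that would be missing anyway or are already in hand.

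**Conclusion.** The point holds and should be fixed. For each patient withdrawn under the rule, obtainable primary data go uncollected for a reason that can depend on arm or outcome, and the analysis section does not say how to deal with it. The POD 1 QoR-40 is exposed only through withdrawals before POD 1; the later LPS sample is exposed more widely; the perfusion recording is not lost through later conversion.

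Size and direction are not known. The bias could favour or mask an effect. The moderate cases amount to less than 1 point against a 10-point target, and a few tenths of a percentage point on the 2.5% LPS threshold. The 7 v 3 cases use the whole replacement allowance and have no documentary basis. All these figures rest on assumed splits and gaps, the SDs of section 4.4, and 48 analysed per arm.

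**What to change.** **Section 8.3.** Keep converted patients and questionnaire non-responders in the study with all remaining scheduled assessments. Stop follow-up only when consent is withdrawn, and keep data already collected. Limit replacement to patients who never start surgery, with that decision made blind to allocation. Report withdrawals and replacements by arm, time and reason. Add a sentence that ending study follow-up does not override the adverse-event follow-up in 9.4.

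**Section 10.** Analyse all randomised patients who start surgery in their assigned arm, conversions included, and report pre-operative exits by arm. State a missing-data method for the primary endpoints that uses the baseline and 24-hour data where they exist (multiple imputation is one option, not the only one), with a sensitivity analysis for values not missing at random. Any analysis without conversions should be a sensitivity analysis only.

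**Cost.** Wording and modest analysis work; the assessments are already scheduled. Power is slightly lower if losses are not replaced (t-test):

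| Analysed per arm | QoR-40 | IL-6 | IL-10 |
|---|---|---|---|
| 48 v 48 | 89.8% | 91.7% | 93.0% |
| 43 v 43 (10 lost evenly) | 86.3% | 88.2% | 89.8% |
| 48 v 38 (10 lost from one arm) | 85.9% | 87.7% | 89.4% |
| 38 v 38 (20 lost) | 81.8% | 83.5% | 85.4% |

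The last row matters because 10 caps replacements, not withdrawals. Actual losses should be smaller, since pre-operative exits are still replaced and converted patients contribute data. Keeping lower-scoring patients adds some noise: if 4% of each arm score 20 points lower, the SD is √(225 + 0.04 × 0.96 × 400) = 15.5, and QoR-40 power at 48 per arm is 88%.
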